### **13. Parental Consent and Children's Assent**

Consent from parents or legal guardians and assent from children should be sought in ensuring the ethical participation of children with cancer in this study.

Informed consent will be obtained from the parents or legal guardians of all participants prior to enrollment. Full information about the purpose of the study, along with the intervention procedures, expected duration, risks involved and possible benefits will be provided. Clarity about data collection, the voluntary aspect, and the right to withdraw their child is communicated both verbally and in writing. Participation in the study will not affect the medical treatment received at HKCH. Parents or legal guardians will be informed of confidentiality measures and mild risks, including slight emotional upsets from talking about sleep problems. They will maintain the right to ask questions and sign the consent form only after indicating full understanding and agreement.

Apart from parental consent, age-appropriate assent will be sought from children aged 6 years and older, recognizing their capability of understanding the research. The assent process will be adjusted to fit the child's age and health. Since children with cancer may be more familiar with medical contexts, the explanation will consider their experiences while remaining concise and engaging. Research staff will use simple, age-appropriate language to describe what process would be involved, including answering questions about sleep through their parents/legal guardians or research staff. Children will be

reassured that no invasive or painful procedures, that they can stop at any time, and their decision will not impact on their treatment or care. Depending on children's ability and preference, assent can be documented via signature or recorded verbally, ensuring their willingness is acknowledged. If a child expresses reluctance or distress, even with parents or level guardian's approval, their involvement will be discontinued to prioritize their well-being.

#### **14. Ethical Approval and Considerations**

Ethical approval from the Joint CUHK-NTEC Clinical Research Ethics Committee (CREC) and Hospital Authority Central Institutional Review Board (IRB) will be obtained before any data collection. The process helps guarantee that the research process, participant recruitment and data control follow ethical guidelines. The CREC and IRB will assess that there are more benefits to the study than risks, ensuring not to cause additional stress or pain to the participants. Parents or legal guardians should be provided with the details needed for informed consent and assent would be sought for children between the ages of 6 and 12 according to HKCH recommendations. All participants and their families will be fully informed about the study's purposes and be given the choice to withdraw from it without any changes to their care.

In order to ensure fairness, participants of the waitlist control group will be given access to the Dreamcatchers Programme once the final follow-up assessment is completed. As a result, all children attending the study are able to get the benefits, regardless of which group they were placed in.

The issue of confidentiality will be solved by recording the data in a manner that does not allow the participants to be identified (i.e. using a non-recognizable code for each patient). The study will be conducted in compliance with Declaration of Helsinki.

#### **15. Significance of the Study**

The Dreamcatchers Programme has significant implications for nursing practice and the care of pediatric oncology patients. This intervention aims to increase sleep duration by at least 30 minutes (Meltzer et al., 2012), reduce PSQI scores by 2 points or more (Ho et al., 2022), and raise PedsQL scores by 5 points or more (Ji et al., 2011). These improvements are expected to enhance not only the quality of sleep but also the overall

quality of life for young oncology patients.

The intervention programme allows healthcare professionals to opt for safer care practices, which is an important consideration for this vulnerable group. Furthermore, the programme helps nurses gain in-depth knowledge of sleep disturbances and increases their confidence when offering comprehensive care. As a result, nurses are better equipped to support cancer children with sleep disturbances and enhance their overall well-being.

The RCT serves as a foundational step toward in creating a consistent sleep management practice to address the absence of standardized practices in pediatric oncology care in Hong Kong. Positive results from this study will demonstrate the efficacy of the Dreamcatchers Programme in clinical settings, and encourage more extensive studies and wider usage.

The Dreamcatchers Programme seeks to achieve both better health outcomes for patients and to develop proactive, well-rounded sleep care by nurses in the long term. This achievement sets a standard for future improvements in pediatric oncology, so that sleep management will always be part of family-centered care. The programme could greatly benefit pediatric oncology patients, both at a local level and all over the world.

## Appendix I: Summary of Literature

Bibliographic Citation	Intervention	Duration	Category	Effect
Liu et al., 2019	Music therapy + Mindfulness	8 sessions (2.5 – 3 hours per session) for 8 weeks	Complementary + psychoeducational	Sleep quality improved post-intervention and between groups
Sriasihi et al., 2019	Music therapy + Education	15 mins music playing before sleep for 3 days		Sleep quality improved post-intervention and between groups
Zupanec et al., 2017	Relaxation + Education	4 weeks	Psychoeducation + Cognitive behavioural	Increased sleep time for intervention group
Rogers et al., 2019	Relaxation + Education + Stimulus control	5 days (with 90 minutes protected sleep time for stimulus control)		Insignificant differences
Sulistyawati et al., 2021	Muscle relaxation	15 mins session twice per day for 7 days	Cognitive behavioural	Insignificant differences
Khoirunnisa et al., 2019	Muscle relaxation + Exercise	15 mins for 5 days	Cognitive behavioural + Physical	Sleep quality improved post-intervention and between groups
Tanriverdi et al., 2022	Virtual-reality based exercise	45 mins session 2 days per week for 12 weeks	Physical	Insignificant differences
Hinds et al., 2007	Exercise (pedaling bicycle)	30 mins twice daily for 2-4 days		Insignificant differences
Jacobs et al., 2016	Massage	20-30 mins for 2-3 nights	Complementary	Insignificant differences

## Appendix II - Intervention and Data Collection Methods and Procedures

Stage	Description	Assessments/Activities	Participants	Notes
Recruitment and Consent	Recruitment occurs at ambulatory chemotherapy day centers at HKCH. Trained research nurses approach eligible families, provide study details, and obtain informed consent from caregivers and child assent when appropriate.	None	All eligible participants	Consent and assent obtained prior to randomization.
Randomization and Allocation	Participants are randomly assigned to intervention or waitlist control group using concealed block randomization managed by an independent researcher to minimize bias.	None	All participants	Ensures balanced group allocation; performed after consent.
Baseline Assessment (T0)	Conducted at enrollment to establish baseline measures. Assessments include: 
 
Demographic survey (age, gender, cancer type, treatment phase)
 
Chinese PSQI (subjective sleep quality)
 
Chinese PedsQL Cancer Module 3.0 (quality of life)
 
	Demographic survey, Chinese PSQI, Chinese PedsQL Cancer Module v3.0	All participants	Performed after randomization.
Intervention Group: Introductory Session	A total of 60 mins nurse-led group session at education room at HKCH introduces the intervention for up to 10 children and caregivers. includes: 
 
45 mins sleep hygiene education (role of sleep, optimizing sleep environment, addressing poor sleep habits)
 
Demonstration of box-breathing (4-4-4 cycle, 5–10 mins nightly)
 
Demonstration of PMR (tensing/relaxing muscle groups, 10–15 mins nightly)
 
	Sleep diary distribution (intervention group)	Intervention group only	Child-friendly instructions (e.g., “squeeze a lemon” for PMR) ensure engagement.

	
 
• Distribution of sleep diaries with QR code videos for home practice
 
			
Weekly Follow-Ups (Weeks 1–3)	
Weekly in-person sessions at the Integrated Rehabilitation Center reinforce intervention techniques. Nurses:
 
 
• Re-demonstrate box-breathing and PMR
 
• Review sleep diaries to check adherence to nightly practice
 
• Address challenges and clarify techniques
 
	Sleep diary review (intervention group)	Intervention group only	Ensures fidelity and supports adherence. Control group receives general health education to prevent contamination.
Immediate Post-Intervention Assessment (T1)	
Conducted at the end of the 4-week intervention to evaluate short-term effects and adherence. Assessments include:
 
 
• Chinese PSQI (sleep quality)
 
• Chinese PedsQL (quality of life)
 
• Sleep diary review (intervention group adherence)
 
• Satisfaction survey, semi-structured interview (intervention group)
 
	Chinese PSQI, Chinese PedsQL, review of sleep diary (intervention group), satisfaction survey and semi-structured interview (intervention group)	All participants (intervention and control)	Satisfaction survey and semi-structured interview includes Likert-scale and open-ended questions. Sleep diaries collected from intervention group to track exercises adherence.
Regular Follow-Ups (Post-Intervention to 3 Months)	
Monthly follow-up sessions monitor sustained practice and address ongoing challenges for the intervention group. Nurses review sleep diaries and provide support for continued PMR and breathing exercise practice.
	Sleep diary review (intervention group)	Intervention group only	Ensures continued engagement and adherence post-intervention.
Three-Month Follow-Up Assessment (T2)	
Conducted 3 months post-intervention to assess durability of effects. Assessments include:
 
 
• Chinese PSQI (sleep quality)
 
• Chinese PedsQL (quality of life)
 
• Sleep diary review (adherence, sleep patterns, intervention group)
 
	Chinese PSQI, Chinese PedsQL, Sleep diary (intervention group)	All participants	Sleep diaries collected from intervention group to evaluate sustained adherence.

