### 7.1 Randomization and Allocation

The study will arrange participants in intervention and waitlist control groups at a 1:1 ratio through block randomization. A computer will be used to generate blocks for randomization to guarantee all the groups are of equal size and to minimize the risk of allocation bias. The randomization sequence is kept secret in sealed but opaque envelopes and will not be opened until enrollment, therefore lowering the chances of selection bias.

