### 7.2 Blinding Procedures

Given the nature of the intervention, blinding participants and caregivers would not be feasible. However, outcome assessors, especially the nurses responsible for data collection, will remain unaware of group assignments. This single-blind design aims to reduce observer bias during data recording and interpretation.

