## **8. Sampling Method and Sample Size Planning**

A simple random sampling method will be applied to recruit participants from the ambulatory chemotherapy day center of Hong Kong Children's Hospital (HKCH), where a list of all eligible attendees at the center is randomly generated by a computer. The decision to recruit day patients rather than hospitalized patients for the study of the Dreamcatchers Programme is grounded in practical, methodological, and generalizability considerations.

Pediatric oncology patients typically do not remain hospitalized indefinitely. Hospitalizations are often episodic, tied to specific treatment phases (e.g., chemotherapy cycles, management of complications), and vary in duration depending on the individual's condition and progress. In contrast, day patients regularly attend ambulatory chemotherapy day centers for scheduled treatments and are discharged afterwards, providing a more stable recruitment pool. The predictable attendance pattern allows consistent intervention delivery during their visits and facilitates adherence to the intervention schedule (weekly in-person follow-ups) and data collection at baseline (T0), post-intervention (T1), and 3-month follow-up (T2). By recruiting day patients, the study minimizes disruptions caused by fluctuating hospitalization status, ensuring feasibility for this pilot RCT.

Secondly, the Dreamcatchers Programme is designed as a non-pharmacological

intervention intended for use in both hospital and home settings. Recruiting day patients better aligns with the programme's adaptability, allowing the intervention to be tested in the setting where it is most likely to be applied long-term.

Despite hospitalized patients are accessible during their inpatient stay, they face unique environmental constraints (e.g. medical equipment, frequent nursing interruptions) that may limit the applicability of certain intervention components, such as creating a sleep-conducive environment. These hospital-specific barriers could confound results and obscure the intervention's true potential in home settings. Day patients, practicing the intervention at home, provide a more representative sample for evaluating its generalizability, as their sleep environment reflect those experienced by pediatric oncology patients post-treatment or during survivorship.

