### **10.1 Participant Recruitment**

Participants will be recruited at ambulatory chemotherapy day centers at HKCH. Trained personnels will approach eligible families, provide study details, and obtain informed consent from parents/legal guardians as well as child assent when appropriate. After consent is obtained, participants will be randomly assigned to either the intervention group or the waitlist control group using a concealed block randomization method, managed by an independent researcher to minimize bias.

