### **10.2 Baseline Assessment (T0)**

At enrollment, all participants will complete the following assessments: demographic survey for data on age, gender, cancer type, and treatment phase, Chinese version of the PSQI for evaluating subjective sleep quality, Chinese PedsQL Cancer Module 3.0 for assessing quality of life, and sleep diary to track sleep patterns and exercise frequency (only for intervention group).

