### **11. Instruments**

A combination of subjective instruments will be used in this study to capture a comprehensive understanding of the participants' sleep quality and overall well-being. The selected tools have been validated for use in pediatric populations and adapted for Chinese children. The authors of the Chinese versions of the PSQI and the PedsQL Cancer Module 3.0 have been contacted and have provided these instruments for use in this study.

The decision to utilize subjective measures rather than objective tools like wrist actigraphy, which focuses on what patients feel and experience, and offers more practical and suitable ways to meet the special requirements of this group. Objective

tools like wrist actigraphy, require wearing devices for a period that may cause discomfort or anxiety, especially for those with medical devices or skin sensitivities. Young children might remove these devices during sleep or play, leading to incomplete data. It is not necessary to spend significant resources on logistics and finances for actigraphy in a pilot study. Alternatively, sleep diaries and the PSQI provide insights into the pattern and quality of participant's sleep. The reliability, validity, and feasibility of each instrument have been carefully considered to minimize participant burden while maximizing data quality.

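### Appendix II takes the baseline PSQI and PedsQL after randomization although families are not blinded; T0 should come before allocation

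*Protocol*

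**What the plan says.** Appendix II lists the stages in the order consent, randomization, baseline (T0). The T0 row contains the demographic survey, the PSQI (primary outcome) and the PedsQL Cancer Module (secondary outcome) for all participants, and its note reads "Performed after randomization".

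The body text gives no other order. Section 10.1 says "After consent is obtained, participants will be randomly assigned to either the intervention group or the waitlist control group". Section 7.1 says the allocation envelopes "will not be opened until enrollment", and section 10.2 also places T0 at enrolment.

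On blinding, section 7.2 states that "blinding participants and caregivers would not be feasible"; only the outcome assessors are kept unaware of the arm. On measurement, section 11 says "A combination of subjective instruments will be used in this study", and section 13 describes the child's part as "including answering questions about sleep through their parents/legal guardians or research staff".

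Section 12 compares PSQI and PedsQL scores between groups at T1 and T2 by independent t-tests. It also uses repeated-measures ANOVA for group-by-time effects, with attention to change from baseline.

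On eligibility, section 8.1 requires a PSQI global score of at least 5. Section 8 samples from the day centre, "where a list of all eligible attendees at the center is randomly generated by a computer", and sections 8.1 and 10.1 speak of approaching families who are already eligible.

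**The concern.** A baseline is useful in a randomized comparison because the allocation cannot have influenced it. Once the envelope is open, a child or parent who knows the arm may rate the past month's sleep differently. A family about to start the programme might stress the problem, and a family placed on the waitlist might do the same out of disappointment. The direction therefore cannot be predicted. Blinded nurses do not remove this, because the answers come from the family. What is at stake is the preliminary effect estimate based on change from baseline. It cannot be repaired once baselines have been collected after allocation.

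A smaller question follows from the same schedule. The entry criterion is a PSQI score, but the first PSQI that the protocol schedules is the one taken after allocation.

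**Working it through.** **1. Order of events, place by place**

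| Place | What it fixes |
|---|---|
| Appendix II, stage order and T0 note | Consent, then randomization, then T0 |
| 10.1 | Randomization follows consent; no measurement is placed between them |
| 7.1 | Envelopes stay closed until enrolment |
| 10.2 | T0 takes place at enrolment; no order relative to the envelope |

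Only Appendix II states an order, and nothing contradicts it. No section says when families are told their arm. The T0 answers can therefore be given with the arm known, though they need not be.

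**2. How a T0 shift reaches the analyses**

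Let D1 and D2 be the true group differences at T1 and T2. Let e0, e1 and e2 be the between-arm differences in reporting caused by knowing the arm at T0, T1 and T2. The expected contrasts are:

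- T1−T0: D1 + e1 − e0
- T2−T0: D2 + e2 − e0
- t-test at T1: D1 + e1
- t-test at T2: D2 + e2

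Three cases:

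- Shift at T0 only (e1 = e2 = 0): both change contrasts are wrong by e0; both t-tests are wrong by 0.
- Equal shift at all three times: the change contrasts are wrong by 0; the t-tests are wrong by the shift.
- T0 taken before allocation (e0 = 0): the change contrasts carry e1 or e2, as the t-tests do.

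The one-for-one result applies to the two change contrasts. The overall group-by-time F test is also disturbed by a T0-only shift, but it is not a simple difference and has no such one-for-one reading.

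**3. Scale**

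The documents give no size for e0. The only yardstick is the 2-point PSQI reduction in section 15. Each 0.1 point is 0.1/2 = 5% of it. If the shift were 0.5 to 1 point, which is an assumption for illustration only, it would be 0.5/2 = 25% to 1/2 = 50%.

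**4. Eligibility**

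Sections 8, 8.1 and 10.1 and the recruitment row of Appendix II all treat families as eligible before approach, and eligibility includes PSQI ≥5. That implies an earlier PSQI. Yet Appendix II lists no assessment at the recruitment or randomization stage, and T0 is the first PSQI described. The screening step is implied but not named.

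**5. Side effect of using one PSQI as both screen and baseline**

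Within-arm change would include regression to the mean of about (1 − r) × (mean of selected children − mean of all screened). The gap between the two means is assumed to be 1 to 3 points.

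- r = 0.90 (test-retest ICC in 11.1): 0.1 × 1 = 0.1 to 0.1 × 3 = 0.3 points.
- r = 0.6 (assumed, for the longer interval to T1 or T2): 0.4 × 1 = 0.4 to 0.4 × 3 = 1.2 points.

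The expected amount is the same in both arms, so between-group contrasts are not biased.

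**The case against.** The strongest reply is that little harm is shown. T0 precedes the introductory session, so the baseline is untreated; the PSQI asks about the past month, which lies before allocation; the nurses collecting data are blinded; and section 8.2 says the pilot is not sized for hypothesis testing. The size of any shift is assumed. Under an equal shift at all three visits, the present order even makes the bias cancel in the change scores.

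Much of this limits the point without removing it. An untreated baseline can still be reported differently by someone who knows the arm, and recall of a past month is a judgement made at the time of asking. Assessor blinding does not reach answers given by the family. The cancellation needs the shift to be the same at T0 as later, which nobody can verify. What stands is that the benefit of reordering is partial: T1 and T2 reports remain unblinded.

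Two stronger readings are tempting. A reader might infer from the intervention-only sleep diary in 10.2 that families certainly know their arm at T0. That does not follow: Appendix II hands out diaries at the later introductory session, and 10.2 may only be saying who receives one. A reader might also infer that children scoring below 5 will be randomized. The text places eligibility before approach, so it shows an unnamed screening step and not a rule that lets ineligible children in.

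**Conclusion.** The point holds in a limited form. Appendix II explicitly puts the subjective baseline after allocation in a trial with unblinded families, and no other section corrects it. A reporting shift confined to T0 would pass in full into the T1−T0 and T2−T0 group contrasts. Its size and direction are unknown, and the percentages of the 2-point target are a scale, not an estimate of bias. It would not affect the independent t-tests at T1 and T2, so the documents do not support saying that every efficacy comparison is compromised. The missing name for the screening PSQI is a secondary clarification. The order should be corrected before enrolment begins; in a pilot it bears on the preliminary effect estimate and does not invalidate the study.

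**What to change.** In Appendix II, move the T0 row above the Randomization and Allocation row and delete its timing note. In 10.1 and 10.2, state the order: consent and assent; then demographic survey, PSQI and PedsQL; then opening of the envelope. Align the enrolment wording in 7.1 with this.

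Name the PSQI that confirms a global score of at least 5 before the envelope is opened: either a screening PSQI or the pre-allocation T0 itself. If one PSQI does both jobs, say that within-arm change includes regression to the mean and that only between-group contrasts will be interpreted. A separate screening PSQI reduces that effect.

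Reconcile who keeps the sleep diary and from when. Section 10.2 lists it at T0 for the intervention group, 11.3 has participants in general keep it with only the exercise-adherence part specific to the intervention group, and Appendix II distributes it to the intervention group at the introductory session. Whatever is decided, keep arm-specific material out of the pre-allocation T0 pack.

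The cost is a wording amendment. The planned number is unchanged: 30/0.9 = 33.3, rounded up to 34 per arm, 68 in total. Some families may complete a PSQI and not be randomized, and a separate screen adds one questionnaire. The change protects the baseline only; it does nothing for unblinded reporting at T1 and T2.

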## 7. Study Design

This study is structured as a pilot prospective and randomized controlled trial (RCT) with a 1:1 allocation to either the intervention group or waitlist control group. The intervention group will receive the Dreamcatchers Programme, including sleep hygiene education, PMR, and breathing control exercises, which will be delivered over 4 weeks with weekly in-person follow-ups. The waitlist control group will continue to receive routine hospital support and pediatric oncology health information (e.g., neutropenic diet tips) to maintain engagement without sleep-specific strategies. The trial will span 4 weeks, followed by a 3-month follow-up to assess the sustainability of outcomes.

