### **7.4 Duration**

The intervention will last for 4 weeks, with data collection points at baseline (T0), immediately post-intervention (T1), and 3 months post-intervention (T2) to evaluate both short-term and sustained effects.

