### **9.3. Breathing Exercises**

Breathing exercises will also be demonstrated and advised to be used before bedtime, aiming to reduce physiological arousal and promote relaxation through slowing down breathing rate, amplifying vagus nerve activity and normalizing stress responses (Chen et al., 2016; Chui et al., 2021). This intervention will specifically utilize diaphragmatic breathing control exercises, which are shown to enhance tidal volume and regulate breathing patterns (Zaccaro et al., 2018). The breathing routine, incorporating box breathing techniques, will last 5-10 minutes and is to be practiced as part of the children's wind-down routine before sleep (Murphy, 2019).

To support consistent practice, a video recording of the PMR and breathing exercises will be provided via QR code with reference to Student Health Service's (2016) materials, integrated into the sleep diaries for easy reference by patients and caregivers.

The participants will be supported after the first introductory session through weekly follow-up sessions for four weeks. These sessions are meant to repeat and practice the techniques learnt, solve any doubts, and monitor participants' sleep hygiene practices. Regular check-ups help to maintain contact and offer support to everyone involved in the treatment.

Nurses will play a key role in delivering sleep hygiene education, demonstrating exercises to patients and caregivers, and conducting follow-up sessions. The principal investigator will train nurses covering sleep hygiene principles, techniques of breathing and PMR exercises, instructions on charting the sleep diary. Trained nurses will conduct mock demonstrations of the group education session and individual exercise demonstrations with their peers. The entire training programme

will take around one week before the actual implementation of the intervention. Trained nursing staff then lead the group education session covering sleep hygiene principles, techniques of breathing and PMR exercises.

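### T2 is described as durability after a 4-week intervention, but Appendix II gives the intervention arm alone monthly nurse support between T1 and T2

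*Protocol*

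**What the plan says.** The body of the Protocol describes a programme that stops at week 4. Section 7 has it "which will be delivered over 4 weeks with weekly in-person follow-ups", "followed by a 3-month follow-up to assess the sustainability of outcomes". Section 7.4 states: "The intervention will last for 4 weeks", and puts T2 at 3 months post-intervention, to look at sustained as well as short-term effects. Section 9.3 sets out the nurse contact: "The participants will be supported after the first introductory session through weekly follow-up sessions for four weeks". Section 10.4 gives durability as the purpose of T2, and the T2 row of Appendix II repeats it: "Conducted 3 months post-intervention to assess durability of effects".

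Appendix II also has a row for the period from the end of the intervention to 3 months, restricted to the intervention group. It reads: "Monthly follow-up sessions monitor sustained practice and address ongoing challenges for the intervention group". It continues: "Nurses review sleep diaries and provide support for continued PMR and breathing exercise practice". The note to that row gives the aim: "Ensures continued engagement and adherence post-intervention". Neither the number nor the dates of these sessions are given.

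Under Section 7 the waitlist arm receives routine support and general health information with nothing specific to sleep. Under Section 14 it is offered the programme only after the final follow-up assessment.

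**The concern.** A durability assessment asks how much of an effect remains after delivery has ended. If nurses are still helping families with the exercises during the follow-up, in one arm only, a T2 difference may reflect the earlier 4 weeks, the continuing support, or both.

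This matters because T2 carries weight. Section 5 names it alongside T1 in both the primary and the secondary hypothesis, and Section 12 plans between-group tests at both time points. Section 2.2 lists the lack of long-term evaluation as a gap in the literature, so a claim of sustained benefit would be noticed. A later trial or service that offered only the 4 weeks could not rely on a T2 result obtained with monthly support in place.

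**Working it through.** No figure in the plan bears on this point, so the check is mainly a comparison of sections.

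**1. When does delivery end?** By Sections 7, 7.4 and 9.3, at week 4. By Appendix II, nurse contact in the intervention arm goes on at monthly intervals towards 3 months.

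**2. Is the monthly contact delivery or only monitoring?** The weekly row of Appendix II gives nurses three tasks: demonstrating the techniques again, reviewing diaries, and dealing with difficulties and clarifying technique. The monthly row keeps the diary review and the help with difficulties and adds support for continued practice. Repeat demonstration is not listed. The stated aim is to keep engagement and adherence up. This is a lighter form of the same support, and more than data collection.

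**3. Does the control arm have a counterpart?** No. The monthly row is for the intervention group only, and no matching contact between T1 and T2 is scheduled for the waitlist arm.

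**4. What does each time point compare?**
- T1: 4-week core programme against waitlist.
- T2: 4-week core programme plus monthly support against waitlist.

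No arm receives the core programme without the later support. The trial's data therefore cannot separate persistence of the 4-week effect from the contribution of the support.

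**5. How close to T2 is the last support?** Assumption: sessions about one month apart after T1, at months 1 and 2, with T2 at month 3. Last support to T2 = 3 − 2 = 1 month, against the 3 months that the post-intervention label suggests. Section 11.1 says the PSQI covers the past month, so on this assumption the T2 recall period starts at about the last supported session.

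**6. How many sessions fall after week 4?** On the same assumption, 2. Sessions within the 4 weeks: 1 introductory + 3 weekly = 4 (Appendix II), or 1 + 4 = 5 (Section 9.3). Share after week 4: 2/(4 + 2) = 33%, or 2/(5 + 2) = 29%. These count sessions only. They do not measure dose, since the length of the monthly sessions is not given, and they say nothing about the size of an effect.

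**The case against.** The strongest reply is that the Protocol never says T2 measures unaided persistence. Its terms are sustainability, sustained effects and durability. The programme teaches skills for nightly home practice, Section 9 describes it as including follow-up, and the T2 row collects diaries to look at sustained adherence. Durability under lightly supported practice is a coherent question. The support is also disclosed: Section 10 points to Appendix II, whose row states frequency, arm, content and purpose. Section 9.3 also has a general line about regular check-ups.

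Much of this stands. Supported durability is a legitimate target, and anyone following Appendix II would deliver the sessions and could report them. What does not stand is the label. Section 7.4 and the T2 row place T2 3 months post-intervention, which tells a reader that delivery has ended. The check-ups line closes a paragraph on weekly sessions for four weeks and sets no later schedule. The two parts of the Protocol define different interventions, and the meaning of T2 depends on which is used.

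It is also fair to say that the harm is confined to interpretation, in a pilot that Section 8.2 says was not sized for hypothesis testing.

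**Conclusion.** The point holds as an inconsistency in the definition of the intervention that changes what T2 can show. T2 estimates the effect of the 4-week core programme plus monthly support against waitlist; it does not show what remains after support stops. It should be corrected, at little cost.

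Three stronger readings are tempting, and the documents support none of them:
- A reader might infer that the T2 comparison is invalid. It is not: the arms are randomised and the contrast is a fair one for the whole package. T1 and the planned between-group tests are unaffected.
- A reader might infer that support runs right up to T2. That needs a third monthly session at month 3, which may simply be the T2 visit, whose own row already includes a diary review. The Protocol does not settle it. The 1-month gap itself rests on the assumption of sessions at months 1 and 2.
- A reader might infer that the T2 effect is inflated by some definite amount. The documents give nothing from which to size the influence of the monthly support on the PSQI.

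**What to change.** Keep the 4-week core programme, and keep T1 as the assessment at its end, so that the T1 labels stay correct. Add the monthly support phase to Sections 7, 7.4 and 9.3, stating that it is for the intervention arm and giving the number and timing of the sessions. In Sections 7, 7.4, 10.4 and the T2 row of Appendix II, describe T2 as the effect 3 months after the core programme with continued monthly support, rather than durability after the intervention ends.

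This is wording only: no added patients, visits or assessments. The cost is a narrower T2 claim.

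Only if unaided durability is the intended question, drop the active support between T1 and T2 and keep diary collection alone. That would make the durability wording accurate, but it removes sessions meant to keep families involved, and engagement may suffer.
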